4.2.4. Secondary Efficacy Endpoints

4.2.4.1. Definition

Formulae to be used for derived variables, including data conversions, are provided in [Table 1](#). In the derivation of durations described below, no imputation of the start and/or end date/time will be performed.

Table 1. Calculations and Conversion Formulae

Measurement	Formula
Length of hospital stay (hours) [Time-to event]	(Date and time of event or censoring - date and time of first dose of study drug)/3600, rounded to one decimal
Time to readiness for discharge (hours) [Time-to-event]	Subjects who complete or withdraw from the study prior to the event will be censored at the date of completion or withdrawal. If the time is not available they will be censored at 12:00. In case of death prior to an event the time of death will be taken as censoring time (or 12:00 if not available).
Length of hospital stay since hospital admission (hours) [Time-to event]	(Date and time of event or censoring - date and time of hospital admission)/3600, rounded to one decimal
Time to readiness for discharge since hospital admission (hours) [Time-to-event]	Subjects who complete or withdraw from the study prior to the event will be censored at the date of completion or withdrawal. If the time is not available they will be censored at 12:00. In case of death prior to an event the time of death will be taken as censoring time (or 12:00 if not available).
ICU duration of stay (hours) [Duration]	sum of [(end date and time of event - start date and time of event)/3600], rounded to one decimal
Duration of supplemental oxygen (hours) [Duration] (3 separate parameters: supplemental oxygen, invasive ventilator, non-invasive ventilator)	If the end date is missing, the end date is considered to be after study completion or withdrawal. If the initial start time is prior to the first dose of study drug, the duration prior to the first dose of study drug will be deducted from the overall duration.
Need for feeding, hydration by IV catheter/enteral tube (hours) [Duration] (2 separate parameters)	If the end date and time is after the study completion/discontinuation, the duration after the date and time of study completion/discontinuation will be deducted from the overall duration. If the time is not available it will be put at 12:00.
Time to end of Oxygen supplementation (hours)	(Date and time of event or censoring - date and time of first dose of


[Time-to-event] (3 separate parameters: overall, invasive, non-invasive)
 
Time to end of supplementation feeding, hydration (hours) [Time-to-event] (2 separate parameters)
	
study drug)/3600, rounded to one decimal
 
The event is defined as the last end date and time of the measured parameter (supplemental oxygen, invasive oxygen, non-invasive oxygen, feeding or hydration). If this date is missing, the end date is considered to be after study completion or withdrawal.
 
Subjects who complete or withdraw from the study prior to the last end date and time of the measured parameter will be censored at the date of completion or withdrawal. If the time is not available they will be censored at 12:00. In case of death prior to the last end date and time of the measured parameter, the time of death will be taken as censoring time (or 12:00 if not available).
 
If no oxygen supplementation, supplemental feeding or hydration was necessary post baseline, the value will be set to 0.

Time point of SpO2 \geq 93% on room air
	
The first time point with SpO2 \geq 93%, where no supplemental oxygen supplementation is given at or after this time point and where no value $<$ 93% are measured after this time point.

Time to SpO2 \geq 93% (hours) on room air [Time-to-event]
	
minimum[date and time of time point with SpO2 \geq 93% on room air, date and time of last SpO2 measurement] - date and time of first dose of study drug)/3600[†], rounded to one decimal
 
Subjects with SpO2$<$93% on room air or who are still on oxygen supplementation at the last SpO2 assessment will be censored at the date and time of the last SpO2 assessment.
 
This parameter will only be calculated for subjects who were not on supplemental oxygen prior to current hospitalization

Time point of return to pre-RSV disease level (hours) for HR, RR, SpO2 (3 separate parameters)
	
The first time point where it is indicated by the investigator that the observed value is normal for the subject, and for none of the time points after this point in time the values are indicated to be abnormal for the subject (separate for HR, RR or SpO2).


Time to return to pre-RSV disease level (hours) for HR, RR, SpO2 [Time-to-event]
	
(minimum[date and time of time point of return to pre-RSV disease level, date and time of last measurement] - date and time of first dose of study drug)/3600, rounded to one decimal
 
If none of the values are indicated to be abnormal for the subject, this value will be set at time 0.
 
Subjects with an abnormal value at the last assessment will be censored. Subjects for which this last assessment is the baseline

	assessment will be censored at time 0.
Time to return to pre-RSV disease feeding status (hours) [Time-to-event]	
(Date and time of event or censoring - date and time of first dose of study drug)/3600, rounded to one decimal
 
All subjects are assumed to have no supplemental feeding pre-RSV.
 
The event is defined as the last available end date and time supplemental feeding was provided. If this date is missing, the end date is considered to be after study completion or withdrawal
 
Subjects who complete or withdraw from the study prior to the event will be censored at the date of completion or withdrawal. If the time is not available they will be censored at 12:00. In case of death prior to an event the time of death will be taken as censoring time (or 12:00 if not available).
 
If no supplemental feeding was necessary post baseline, the value will be set to 0.

Time to Clinical Stability [Time-to-event]	
maximum[time to return to pre-RSV disease level for SpO₂, RR and HR, feeding]
 
Subject will be censored if the subject is censored for at least 1 of the 4 time to parameters at the minimum of the available data. If no data are available the time will be censored at 0 hours.

Time point of return to normal temperature (hours) [Time-to-event]	
All subjects are assumed to have a normal temperature level pre-RSV disease
 
Time point of return to pre-RSV disease level temperature is defined as the first time point with a normal temperature and no time points after that time point with an abnormal value.
 
The normal limits to be used are:
 
 - Axillary: 36.1 – 38.0 - Forhead: 36.1 – 38.0

	
 - Oral: 36.1 – 38.0 - Rectal: ≤ 37.2 - Tympanic: ≤ 37.8 
If there were no abnormal values post baseline, the value will be set at 0 hours.

Time to normal temperature (hours) [Time-to event]	
Minimum[date and time of Time of return to pre-RSV disease level temperature, date and time of last measurement] - date and time of first dose of study drug)/3600[†], rounded to one decimal
 
If none of the values are abnormal for the subject, this value will be set at time 0.
 
Subjects with an abnormal value at the last assessment will be censored. Subjects for which this last assessment is the baseline assessment will be censored at time 0.

Time point of return to pre-RSV functional status (KATZ ADL score)	
The first time point where the KATZ ADL score is equal or higher than the pre-RSV disease KATZ ADL score and no lower scores are measured after this time point.
 
Functional status is the total points on the KATZ Index of Independence in Activities of Daily Living (KATZ ADL score)

Time to return to pre-RSV functional status (KATZ ADL score) (days) [Time-to-event]	
minimum[date and time of time of return to pre-RSV functional status, date and time of last measurement] - date and time of first dose of study drug)/3600, rounded to one decimal
 
If the KATZ ADL score is never lower than the pre-RSV score, this value will be set at time 0.
 
Subjects with a functional status lower than the pre-RSV disease functional status at the last KATZ ADL assessment will be censored. Subjects for which this last assessment is the baseline assessment will be censored at time 0.

Ordinal scale score	
The value as collected in the eCRF on the day of last dose (Day 5/6 depending on timing of LD) will be used as score on the day of last dose. Only in case of a missing score, the score will be calculated based on the available information in the eCRF.
 
The 6 categories to be considered are:

	
 • Death • Admitted to ICU • Non-ICU hospitalization requiring supplemental oxygen • Non-ICU hospitalization not requiring supplemental oxygen • Not hospitalized, unable to resume normal activities • Not hospitalized, resumption of normal activities 
Subjects will receive a score ranging from 1 (=subject died on or before of their day of last dosing) to 6 (=subject was not-hospitalized, resumption of normal activity) depending on his status on day of last dosing
 
For days 3 to 14, the ordinal scale will be calculated on each day, using the algorithm described above.

All-cause mortality	Subjects who died during the study will receive code 1, subjects who survive will receive code 0
Peak viral load	Highest value of viral load at or after the baseline measurement.
Time to peak viral load (hours) [Time-to-event]	
Defined as the relative time in hours from the first dose of study drug until the first time point when the viral load reaches the peak viral load.
 
Subjects for which the peak was reached at the baseline measurement will have time 0.
 
Subjects for whom the peak is reached at the last observed time point will be censored. Subjects for which this last assessment is the baseline assessment will be censored at time 0.

Rate of decline of viral load over the first 24 hours	
calculated as a log decline/24 hours defined as: $(24\text{-hour log viral load after first dose of study drug} - \text{log viral load at baseline}) / (\text{date/time of 24-hour viral load sample} - \text{date/time of baseline viral load})$
 
Note, the 24-hour viral load may not have been measured at exactly 24 hours following first dose, but the actual date/time associated with the 24-hour viral load will be used in computing the viral load slope. In case the 24 hour measurement is not

	available the slope will be calculated using the Day 3 assessment (48 hours), using the same definition. If there is no measurement in that time frame, the slope will not be calculated.
Time to non-detectability (hours) [Time-to-event]	
Defined as the relative time in hours from the first dose of study drug until the first post baseline time point when the viral load reaches non-detectability and no detectable values are measured after this time point.
 
For each subject in the ITT-i it will be assumed that the subject is positive at baseline (even if the value is negative).
 
Subjects whose viral load does not reach non-detectability will be censored at the relative time in hours from the first dose of study drug until this last RSV assessment. Subjects for which this last assessment is the baseline assessment will be censored at time 0.

Time to non-detectability (hours) [interval censored]	The boundaries of the censoring intervals are defined as the number of hours from the start of treatment. The left boundary of the interval is the last positive assessment before the first confirmed negative sample which is not followed by a confirmed positive sample (at baseline every subject is considered positive). If no negative samples are observed, the left boundary will be the last sample obtained. The right boundary of the interval is the first confirmed negative sample which is not followed by a confirmed positive sample. If this is not observed, the interval is right censored. A confirmed positive sample is defined as two consecutive non-negative samples; a confirmed negative sample is defined as two consecutive negative samples. Last obtained sample, whether positive or negative, is always considered confirmed.
Log viral load area under the curve from baseline to 10 days post first dose of study drug ($AUC_{0-10 \text{ days}}$).	
The $AUC_{0-10 \text{ days}}$ will be derived based on trapezoid method:
 $AUC_{0-10 \text{ days}} = AUC_{0-7 \text{ days}} + \frac{3}{2}(y_7 + y_{10})$ 
where y_7 is the log 7 viral load at day 10 and y_{10} is the log 10 viral load at day 10.
 
The following rules will be applied to deal with missing values before calculating the Viral load AUC:
 
 • If the last observations are missing, the last available observation will be carried forward. Unscheduled assessments will be included and will be eligible for

	
carrying forward until Day 10.
 
 In case multiple nasal swabs were taken on a single day the average on the log scale will be used as the value for that subject.
Log viral load area under the curve from baseline to 14 days post first dose of study drug ($AUC_{0-14 \text{ days}}$).	
The $AUC_{0-14 \text{ days}}$ will be derived based on trapezoid method:
 $AUC_{0-14 \text{ days}} = AUC_{0-10 \text{ days}} + \frac{4}{2}(y_{10} + y_{14})$ 
where y_{10} is the log 10 viral load at day 10 and y_{14} is the log 10 viral load at day 14.
 
The following rules will be applied to deal with missing values before calculating the Viral load AUC:
 
 If the last observations are missing, the last available observation will be carried forward until Day 14. In case multiple nasal swabs were taken on a single day the average on the log scale will be used as the value for that subject.

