A secondary endpoint of high interest is the length of hospital stay. The length of hospital stay is in hours and taken from the start of treatment initiation to discharge and to readiness for discharge. The differences of active dose regimens versus placebo treatment will be estimated using the accelerated failure time model using appropriate contrasts; baseline covariates such as stratification factors, absence/presence of other viral or bacterial pathogens, RSV baseline log₁₀ viral load, and time from onset of first symptoms to treatment will be added when of predictive value based on blinded data. Treatment effects versus placebo will be reported as acceleration factors including 95% confidence intervals. Subjects for which no time point could be established (eg, withdrawal of informed consent before reaching the endpoint) will be (right-)censored at the latest time point at which it could be established that the endpoint was not reached. Subjects for whom discharge cannot be considered as a marker of adequate recovery (eg, subjects who die during hospitalization or who are transferred to a care facility with the same level of care as during hospitalization) will be censored at the planned final follow-up visit. No adjustments for multiplicity will be made. Analytical details will be provided in the SAP.

While this clinical endpoint is considered of high interest, the current sample size is determined by considerations on antiviral activity; for length of hospital stay the anticipation is that there will be too much heterogeneity to expect statistically significant separation of active groups versus placebo with the current sample size, even if a numerical trend is anticipated.

The impact of the baseline viral genotype and subtype on the antiviral activity will be explored.

Analysis of the viral sequencing results will be described in the SAP.

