1. INTRODUCTION

This statistical analysis plan (SAP) contains definitions of analysis sets, derived variables and statistical methods for the analysis of efficacy and safety of the investigational compound ALS-008176 (also known as JNJ-64041575). The SAP is to be interpreted in conjunction with the protocol. A detailed analysis plan for the Interim Analysis will be described in the Interim Analysis Plan (IAP). A detailed analysis plan for the pharmacokinetic and pharmacokinetic/pharmacodynamics data will be described in a Clinical Pharmacology Analysis Plan (CPAP).

ALS-008176 is a 3',5'-bisisobutyrate prodrug, which is readily metabolized to the cytidine nucleoside analog, ALS-008112. Subsequently, inside cells, ALS-008112 is efficiently converted to its nucleoside triphosphate, ALS-008136. This nucleoside triphosphate is a potent inhibitor of respiratory syncytial virus (RSV) ribonucleic acid (RNA)-dependent RNA polymerase activity and works via a classic chain termination mechanism. ALS-008144, the uridine metabolite of ALS-008112, is the inactive major metabolite noted in systemic circulation.

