If specified, time-to-events variables will also be compared between each active treatment group and placebo using an accelerated failure time (AFT) model. The distribution to be used will be determined based on the goodness of fit using Akaike's information criterion and will be selected from the following parametric families: lognormal, log-logistic, or Weibull. The AFT model will include the fixed, categorical effects for treatment (with placebo as the reference) and strata, as well as the continuous covariates of baseline \log_{10} viral load. Other covariates may be included when of predictive value, such as smoker (yes/no), presence/absence of co-morbid diseases, presence/absence of co-morbid diseases associated with risk for lower respiratory tract disease, presence/absence of other conditions/therapy of potential interest, days since symptom initiation, RSV subtype, use of corticosteroids, supplemental oxygen at baseline and age as continuous variable. As in the logistic regression, a significance level of 0.05 will be used for a variable to enter the model and a significance value of 0.10 to stay in the model. A summary of information from the final model will include parameter estimates and associated standard errors, estimated accelerated failure time ratios versus placebo and associated 95% confidence intervals, and p-values.

Length of Hospital Stay/Length of Hospital Need

The Length of Hospital Stay/Need (both since treatment initiation and since hospital admission) will be summarized and listed. The Length of Hospital Stay/Need will be analyzed in an exploratory manner using Kaplan-Meier analysis.

Length of Hospital Stay/Need will also be compared between each active treatment group and placebo using an accelerated failure time (AFT) model as described above.

Need and Duration of ICU Stay

The need for ICU stay will be analyzed on the subgroup of subjects who were not in the ICU before the first dose of study medication. The duration in the ICU will be analyzed all subjects and on both the subgroup who were and who were not in the ICU before the first dose of study medication.

The number and percentage of subject with need of ICU stay, and the duration of ICU stay in hours, will be summarized descriptively.

To compare incidence of the need for ICU stay across treatment groups, (exact) logistic regression as described before will be used.

Need and Duration of Oxygen Support, Supplemental Feeding, Supplemental Hydration

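### For length of hospital stay and readiness for discharge, the SAP censors in-hospital deaths at death, the protocol censors them at the planned final visit, and the SAP omits the protocol's rule for same-level transfers.

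*SAP*

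**What the plan says.** Protocol 11.3, under the secondary endpoints, states: "A secondary endpoint of high interest is the length of hospital stay". The time is measured in hours and "taken from the start of treatment initiation to discharge and to readiness for discharge". There are two censoring rules. Subjects with no established time point, such as those who withdraw consent, are censored when last known not to have reached the endpoint. A separate sentence covers subjects for whom discharge does not mark adequate recovery. Its examples are "subjects who die during hospitalization or who are transferred to a care facility with the same level of care as during hospitalization", and these subjects "will be censored at the planned final follow-up visit". Protocol 9.1.4 puts that visit at Day 28.

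SAP 4.2.4.1, Table 1, covers the same two endpoints, counted from first dose and also from admission. Subjects who complete or withdraw are censored on that date. For deaths it states: "In case of death prior to an event the time of death will be taken as censoring time" (12:00 if the time is unknown). The SAP does not mention same-level transfers. SAP 4.2.4.2 then states: "Length of Hospital Stay/Need will also be compared between each active treatment group and placebo using an accelerated failure time (AFT) model".

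**The concern.** For deaths, the protocol and the SAP give different censoring times for the same endpoint, and the SAP states no reason. The protocol leaves analytical details to the SAP, but it fixes this rule itself and explains it, so the SAP reverses a rule rather than filling a gap. The SAP introduction states: "The SAP is to be interpreted in conjunction with the protocol". That can supply the missing transfer rule. It cannot settle two incompatible instructions on deaths.

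Censoring at death treats the death as non-informative, as if the patient would have gone on to be discharged like those still in hospital. The protocol rule keeps the patient as not discharged through Day 28. If mortality differs between arms, the SAP rule therefore weakens its effect on the time ratio. It can soften a signal of harm or hide part of a benefit.

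A programmer working from Table 1 alone would by default count a same-level transfer as a discharge, which the protocol rules out.

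**Working it through.** The documents give no stay distribution, event count or power for this endpoint, so there is no stated figure to reproduce. The contradiction rests on the text. The simulation only indicates size.

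**The two rules**

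| Subject | Protocol 11.3 | SAP Table 1 |
|---|---|---|
| Dies in hospital | Censored at planned final visit (Day 28) | Censored at time of death |
| Transferred at same level of care | Censored at planned final visit | No rule |
| Withdraws before the event | Censored when last known not to have reached the endpoint | Censored at withdrawal |

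**Model.** Lognormal AFT, log T = μ + βx + σε, with discharge as the event and time ratio exp(β) for active versus placebo (above 1 means a longer stay). A discharge contributes its density to the likelihood. A censored subject contributes P(T > c). For a death, c is the death time under the SAP rule and 27 × 24 = 648 h under the protocol rule.

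**One death, at 96 h.** Assume a median stay of 168 h and an SD of log stay of 0.7.
- SAP rule: ln(96/168)/0.7 = −0.80, so P(T > 96) = 0.79. The death has little influence on the fit.
- Protocol rule: ln(648/168)/0.7 = 1.93, so P(T > 648) = 0.027. The death pulls that arm towards a longer stay.

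**Inputs.** 30 per arm (protocol 3.1). The following are assumptions: the same stay distribution in survivors of both arms, as above; deaths uniform from 24 h to Day 7, 14 or 27; and all mortality splits. The 13.8% is the highest 60-day rate cited in protocol 1.2, so it is an upper case. At 30 per arm, 5% and 13.8% correspond to 1.5 and 4.1 expected deaths. Both rules were applied to the same data, with 800 trials per scenario. The Monte Carlo SE of the mean log ratio is 0.007 to 0.009.

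| Placebo v active mortality | Protocol rule | SAP rule |
|---|---|---|
| 3.3% v 6.7% (about 1 v 2 deaths), to Day 14 | 1.06 | 1.02 |
| 5% v 13.8%, all in hospital, to Day 7 | 1.18 | 1.03 |
| Same, to Day 14 | 1.18 | 1.06 |
| Same, to Day 27 | 1.18 | 1.10 |
| 5% v 13.8%, death counted only if it precedes an independent discharge time, to Day 7 / 14 / 27 | 1.11 / 1.06 / 1.03 | 1.00 |
| 13.8% in both arms | 1.00 to 1.01 | 1.00 to 1.01 |

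**Against sampling error.** The SD of one trial's log estimate is about 0.19 (SAP rule) to 0.23 (protocol rule).
- Upper case to Day 14: ln 1.18 − ln 1.06 = 0.107, about half of one SD.
- Moderate case: ln 1.06 − ln 1.02 = 0.038, about one fifth of one SD.

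**Other stay assumptions**
- Median 144 h, 5% v 13.8%, all in hospital: 1.20 (protocol) against 1.04, 1.07 and 1.12 (SAP).
- Median 120 h, log SD 0.8, deaths 2 to 14 days after first dose, 40,000 per arm: 5% v 13.8% gives 1.20 against 1.08, and 5% v 10% gives 1.11 against 1.05. With the extra deaths on placebo the direction reverses: 13.8% v 5% gives 0.83 against 0.92, and 10% v 5% gives 0.90 against 0.96. Equal mortality gives about 1 under both rules.

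**The case against.** The text conflict is not in dispute. The case on the other side concerns weight and interpretation.

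- **Low stakes.** Protocol 11.3 applies no multiplicity adjustment here and expects heterogeneity to prevent statistically significant separation at this sample size. Mortality has its own comparison (SAP 4.2.4.2), and death is the worst ordinal-scale category. This stands and limits the severity.
- **The upper case is extreme.** A 60-day rate from other settings is applied as in-hospital mortality by Day 28, to one arm only, in a trial that excludes patients not expected to survive 48 hours. This also stands. The moderate case is the better guide to likely size.
- **The protocol rule is not more correct statistically.** Survivors were simulated with identical stays, so the SAP rule lies nearer to the true ratio of 1.00 for discharge among survivors. The protocol rule also right-censors deaths, so the AFT model still assumes a discharge after Day 28. This is fair: the two rules answer different questions. The protocol rule has priority because it was prespecified with a reason and the SAP departs from it without one.
- **It may be a drafting lag.** The SAP still has the age limit of 50 and an interim at 45 subjects randomized, both changed by protocol Amendment 2. The amendment log does not mention this censoring rule, so the cause cannot be determined. A lag would explain the conflict but not resolve it.
- **The transfer part is an omission.** Agreed. It needs a derivation written out and is secondary to the conflict on deaths.

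**Conclusion.** The concern holds. For in-hospital deaths the SAP contradicts a rule that the protocol fixes, nothing else in the documents reconciles them, and the transfer rule is missing from the SAP. This should be fixed. The primary analysis is not affected. The effect on the time ratio is nil on average if mortality is equal, small in the moderate case (1.06 against 1.02) and about half of one trial's SD in the upper case with deaths to Day 14 (1.18 against 1.06). Its direction follows the arm with more deaths. These sizes rest on the assumed stay distribution, death timing and mortality splits. The finding of a contradiction rests on the text alone.

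**What to change.** Before unblinding, replace the death sentence in SAP Table 1 for length of stay and time to readiness for discharge. The new text should say that subjects who die in hospital, or are transferred at the same level of care, are not events and are censored at the planned Day 28 visit. Apply it to the admission-based versions as well, for consistency; the protocol states its rule only for the clock that starts at treatment initiation. Keep censoring at death as a sensitivity analysis. If the sponsor prefers censoring at death as the main rule, that departure should be stated and justified before deaths by arm are known, with the protocol rule as the sensitivity analysis.

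Leave the oxygen, feeding and clinical-stability rows of Table 1 unchanged. The protocol rule does not cover them, and protocol 11.3 gives clinical stability its own censoring rule.

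The cost is SAP wording, a small programming change and one sensitivity run. Check that the eCRF records transfer destination and level of care; the documents do not say.
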